Study Protocol with Statistical Analysis Plan (SAP)

Title: Evaluation of the Postoperative Effects of Horizontal Platelet-Rich Fibrin after Impacted Third Molar Extraction: A Randomized Controlled Clinical Study

NCT Number: NCT06244797

Last update/approval date: December 28, 2023 (Ethics Committee and Ministry of Health Approval)

1. Background and Rationale

Impacted mandibular third molars are frequently removed due to complications such as pericoronitis, cyst formation, or damage to adjacent teeth. Postoperative sequelae include pain, swelling, and trismus. Platelet-rich fibrin (PRF) is a second-generation platelet concentrate with regenerative and anti-inflammatory potential. Horizontal PRF (H-PRF), produced via horizontal centrifugation, yields higher concentrations of platelets and leukocytes compared with leukocyte PRF (L-PRF). No randomized controlled trial has directly compared H-PRF and L-PRF in mandibular third molar surgery.

2. Study Objectives

Primary Objective: To evaluate whether H-PRF reduces postoperative swelling compared with L-PRF and control.

Secondary Objectives: To compare effects on pain, trismus, soft tissue healing, analgesic consumption, and quality of life (QoL).

3. Study Design

Design: Prospective, randomized, controlled, double-blind clinical trial.

Setting: Tokat Gaziosmanpaşa University, Faculty of Dentistry, Department of Oral and Maxillofacial Surgery.

Duration: Recruitment and follow-up between January and March 2024.

4. Study Population

Inclusion Criteria:

- Patients aged 18–40 years
- Indication for extraction of mucosally retained mandibular third molars
- ASA I classification
- Signed written informed consent

Exclusion Criteria:

- Systemic disease
- Allergy to penicillin or local anesthetics
- Previous radiotherapy to head and neck
- Requirement for antibiotic prophylaxis
- Presence of pericoronitis
- Inability to attend follow-up visits

5. Randomization and Blinding

Randomization performed via sequentially numbered, opaque sealed envelopes prepared by an independent nurse.

Allocation ratio: 1:1:1 (H-PRF, L-PRF, Control).

Patients and outcome assessor blinded.

Operating surgeon aware of allocation.

6. Interventions

H-PRF Group: 10 mL venous blood centrifuged horizontally (2200 rpm, 8 min) and applied to socket.

L-PRF Group: 10 mL venous blood centrifuged via fixed-angle centrifugation (2700 rpm, 12 min).

Control Group: Standard extraction without PRF application.

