All sockets closed with 3-0 silk sutures.

Standard postoperative medication: dexketoprofen trometamol (25 mg as needed), chlorhexidine mouth rinse (0.12%, twice daily for 7 days). No prophylactic antibiotics prescribed.

7. Outcomes

Primary Outcome: Swelling (linear facial measurements), assessed pre-op, Day 2, Day 7.

Secondary Outcomes:

- Pain (VAS, 0–100 mm), Days 1–7
- Trismus (maximum interincisal distance), baseline, Day 2, Day 7
- Soft tissue healing (Landry index), Days 2 and 7
- Analgesic consumption (daily record)
- QoL (Majid's questionnaire), Days 4 and 7

8. Statistical Analysis Plan (SAP)

Software: IBM SPSS v23

Normality: Shapiro-Wilk test

Categorical variables: Chi-square test

Continuous variables: One-way ANOVA (normal distribution) or Kruskal-Wallis test (non-normal)

Repeated measures: Repeated measures ANOVA with Bonferroni post hoc (normal) or Friedman with Dunn's post hoc (non-normal)

Baseline imbalance: ANCOVA with baseline covariates (for swelling)

Effect sizes: Mean differences with 95% CI, standardized effect sizes reported

Significance level: $p < 0.05$

Missing data: No missing data expected (all 75 randomized completed)

9. Ethical Considerations

Approved by Tokat Gaziosmanpaşa University Clinical Research Ethics Committee (Approval No: 23-KAEK 146).

Additional authorization: Ministry of Health (Decision No: E-57955685-000-224940348).

Registered at ClinicalTrials.gov (NCT06244797).

Written informed consent obtained from all participants.

10. Data Handling

Data anonymized and stored securely.

Analyses conducted according to pre-specified protocol.

Data available upon reasonable request from corresponding author.

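### For non-normal repeated outcomes the named method, Friedman with Dunn's, tests days and not arms, and the Kruskal-Wallis line that could compare arms has no day, summary or multiplicity rule

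*Combined protocol and SAP*

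**What the plan says.** Section 2 states the secondary aim as a comparison: "To compare effects on pain, trismus, soft tissue healing, analgesic consumption, and quality of life (QoL". Section 5 sets up three parallel groups: "Allocation ratio: 1:1:1 (H-PRF, L-PRF, Control".

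Section 7 measures every secondary outcome more than once:
- Pain: "Pain (VAS, 0–100 mm), Days 1–7"
- Analgesics: "Analgesic consumption (daily record", with the number of days not given
- Quality of life: two days (4 and 7)
- Mouth opening: baseline and Days 2 and 7
- Landry index: Days 2 and 7

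Section 8 lists tests by type of data. The branch is chosen by "Normality: Shapiro-Wilk test". Two lines matter here:
- Continuous variables: "One-way ANOVA (normal distribution) or Kruskal-Wallis test (non-normal"
- Repeated measurements: "Repeated measures: Repeated measures ANOVA with Bonferroni post hoc (normal", with the alternative "Friedman with Dunn's post hoc (non-normal"

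Apart from ANCOVA for swelling, no test is tied to a named outcome. No arm-by-day term is mentioned, and no adjustment over days or outcomes is given.

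**The concern.** The two halves of the repeated-measures line are offered as alternatives, but they do not test the same thing. Repeated measures ANOVA can carry arm and arm-by-day. Friedman cannot: its blocks are patients and its treatments are days, so Dunn's pairs after it are pairs of days. A Shapiro-Wilk result would then decide whether the longitudinal analysis can address the trial question at all. Bounded VAS scores and tablet counts may well fail that test.

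In the non-normal branch the arm comparison therefore falls to Kruskal-Wallis, which the plan leaves unspecified. The analyst must choose after the fact between seven daily tests, one chosen day or a weekly summary. Those choices differ in both false-positive rate and power. The point covers the secondary outcomes that section 7 measures repeatedly; swelling has its own ANCOVA line.

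**Working it through.** **1. What Friedman tests.** With n patients, k days and R_j the sum over patients of the within-patient rank of day j:

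Q = [12 / (n k (k+1))] × Σ R_j² − 3n(k+1)

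For pain, pooled over the trial, n = 75 and k = 7, so the multiplier is 12 / (75 × 7 × 8) = 12/4200. Arm appears nowhere in the formula. Adding a constant to all seven scores of every patient in one arm leaves each patient's ranks unchanged, hence every R_j and Q unchanged.

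- Numerical check: a 75 × 7 matrix with 25 rows shifted by a constant gave Q = 6.36, p = 0.384, both before and after.
- The result is exact while scores stay off the ends of the VAS. At the floor a shift creates ties, but that does not turn the test into a comparison of arms.
- With k = 2 (quality of life, Landry index) the test reduces to first day versus second day.

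**2. Behaviour in simulation.** Assumed: 3 arms of 25, seven days, lognormal data, correlation 0.5, 1,000 runs.

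| Situation | Friedman, pooled | Kruskal-Wallis, one day | Kruskal-Wallis, 7-day mean |
|---|---|---|---|
| 1 SD shift in one arm, no time trend | 5.6% | 94% | 99.7% |
| Time trend, no arm effect | 100% | 3.9% | 4.4% |

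Friedman responds to days and is blind to the arm effect.

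**3. What the Kruskal-Wallis line delivers if applied day by day.** The documents give no SD, correlation or expected pain course, so no figure of the plan's own can be reproduced. Inputs:
- 75 randomised and 1:1:1 (sections 8 and 5), hence 75/3 = 25 per arm
- Seven pain days (section 7) and alpha 0.05 (section 8)
- Assumed: VAS falling linearly from 50 to 13 mm, SD 15–20 mm, correlation 0.4–0.8, and a 10 mm benefit in one arm on every day

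Upper reference for seven unadjusted tests if days were independent: 1 − 0.95⁷ = 30.2%. Days within a patient are correlated, so the rate should be lower. Across the assumed SDs and correlations:

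| Kruskal-Wallis procedure for pain | False positives, no arm effect | Power, 10 mm benefit |
|---|---|---|
| Each of 7 days at 0.05, any significant | 16–29% | not comparable |
| Each of 7 days, Bonferroni | 2–5% | 33–79% |
| Once, on the 7-day mean | about 5% | 47–93% |

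At either end of the power range the single summary gains 14 points (47 − 33 and 93 − 79). The Bonferroni false-positive row comes from a separate set of 800 runs per setting under the same assumptions. That set also gave 15–28% for unadjusted daily tests, and power of 36–80% against 48–92%.

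**The case against.** The strongest reply is that section 8 already has a non-normal test of arms. On a natural reading, the continuous-variable line compares groups and the repeated-measures line describes change over time. Friedman then does the job it was built for. The text never says that the repeated-measures line must carry the arm comparison, and it names no arm factor even for the ANOVA. The branch is also conditional on Shapiro-Wilk.

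Much of this stands. A reader might infer that non-normal secondary outcomes are left with no between-arm test; the Kruskal-Wallis line rules that out. A reader might also infer that the trial will compare arms by whether, or when, each shows a significant fall. If that were done, and each of three identical arms had power p for the within-arm contrast, the verdicts would disagree with probability 1 − p³ − (1 − p)³:
- p = 0.8: 1 − 0.512 − 0.008 = 48%
- p = 0.5: 1 − 0.125 − 0.125 = 75%

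No section plans such a comparison, so these figures show only the hazard of misusing within-arm tests. They do not measure the cost of the plan.

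What the reply does not remove is that Kruskal-Wallis has no day, summary, pairwise follow-up or adjustment. Nor is there any non-parametric arm-by-day test to match what the ANOVA branch could provide.

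**Conclusion.** The point holds in a limited form. In the non-normal branch the named longitudinal method tests change over days only and cannot serve the between-arm secondary objectives for any of the five outcomes. That follows from the formula and needs no assumption.

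The between-arm analysis that remains is listed but unspecified. For pain, unadjusted daily use would give a false positive somewhere in about 16–29% of trials. Bonferroni over the days controls this, but costs about 14 points of power at each end of the range compared with one test on the weekly mean. These sizes rest on the assumed SDs, correlations and pain course, and on a benefit that is steady across days; an effect confined to one day would favour the daily tests.

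Confidence is moderate, because the brief text of section 8 allows a reading in which Friedman was meant only for the time course. The plan should be changed, but the point touches secondary outcomes and a conditional branch.

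**What to change.** In section 8, name one between-arm analysis for each repeatedly measured secondary outcome that is non-normal. Suggested text:

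*Arms are compared once on a pre-specified per-patient summary by the Kruskal-Wallis test, followed by Dunn's pairwise comparisons of arms with adjustment. The summaries are mean VAS over Days 1–7, total tablets over a stated period, the mean of the Day 4 and Day 7 quality-of-life scores, change from baseline in mouth opening at a named day, and the Landry score at a named day. The Friedman test describes the time course within arms only; within-arm tests are not used to claim a difference between arms.*

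An alternative is a mixed model with arm, day and arm-by-day, using robust or bootstrap standard errors.

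The cost is SAP wording and a few lines of analysis, with no extra patients or visits. A weekly summary is less sensitive to an effect on a single day; the arm-by-day term covers that if the mixed model is chosen.

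### Section 8 does not say whether baseline ANCOVA is always the between-arm analysis of swelling or only a response to imbalance, and it states no covariate adjustment for trismus

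*Combined protocol and SAP*

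**What the plan says.** Section 7 defines the primary outcome with its visits: "Primary Outcome: Swelling (linear facial measurements), assessed pre-op, Day 2, Day 7". Among the secondary outcomes it lists "Trismus (maximum interincisal distance), baseline, Day 2, Day 7". No other secondary outcome has a listed pre-operative value.

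Section 8 has four lines that bear on how these two outcomes are compared between arms:

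- The general test: "Continuous variables: One-way ANOVA (normal distribution) or Kruskal-Wallis test (non-normal". It has no covariate, and the plan does not say whether it is applied to post-operative values or to changes.
- The repeated-measures line: repeated-measures ANOVA with Bonferroni comparisons, or Friedman with Dunn's comparisons. It names no outcome, no between-arm factor and no interaction.
- The only mention of ANCOVA: "Baseline imbalance: ANCOVA with baseline covariates (for swelling".
- The effect measure: "Effect sizes: Mean differences with 95% CI, standardized effect sizes reported". It does not say whether the differences are adjusted.

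Section 10 adds "Analyses conducted according to pre-specified protocol".

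**The concern.** The ANCOVA line supports two different analyses. As a conditional rule, the default is an unadjusted test, and ANCOVA enters only if the arms differ at baseline by some unstated criterion. As a topic label, ANCOVA is the analysis of swelling in every case. The line speaks of covariates in the plural without naming the pre-op swelling value. It also does not say whether ANCOVA replaces the general test or sits beside it. Section 10 appeals to a pre-specified analysis, yet for the primary outcome the text does not identify which between-arm result that is.

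The restriction to swelling leaves trismus without a stated covariate adjustment, although its baseline is collected.

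Two things are at stake. One is precision: a real difference between H-PRF and the other arms is more likely to be missed if a less efficient test is used. The other is that a reader of the results cannot tell which analysis was meant to be primary.

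**Working it through.** **Inputs from the documents.** Section 8 gives 75 patients and a significance level of 0.05. Section 5 gives "Allocation ratio: 1:1:1 (H-PRF, L-PRF, Control", so 75/3 = 25 per arm if exactly balanced. The documents state no power, effect size, SD or correlation, so there is no planned figure to reproduce.

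**Assumptions.** One arm (H-PRF) differs from the other two by 0.5 SD. The SD is the same at baseline and follow-up. The baseline to follow-up correlation ρ is 0.3, 0.5, 0.7, 0.8 or 0.9. One follow-up day is tested.

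**Variance factor f relative to raw post-operative values**

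- raw value: f = 1, 72 error df
- change from pre-op: f = 2(1−ρ), 72 error df
- ANCOVA on the pre-op value: f = 1−ρ², 71 error df

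Since 1−ρ² = (1−ρ)(1+ρ), the ANCOVA factor is never larger than 1 or than 2(1−ρ). Apart from the one degree of freedom, ANCOVA is at least as precise as either alternative.

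**Omnibus power.** The arm means deviate from the grand mean by 0.333, 0.167 and 0.167 SD in absolute value. The noncentrality is therefore 25 × (0.111 + 2 × 0.0278)/f = 4.167/f. Power is the probability that a noncentral F with 2 and 72 (or 71) df exceeds its 5% critical value, 3.12 (3.13).

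| ρ | f, change | f, ANCOVA | Power raw | Power change | Power ANCOVA | Loss, change | Loss, raw |
|---|---|---|---|---|---|---|---|
| 0.3 | 1.40 | 0.91 | 41.5% | 30.8% | 45.1% | 14 | 4 |
| 0.5 | 1.00 | 0.75 | 41.5% | 41.5% | 53.1% | 12 | 12 |
| 0.7 | 0.60 | 0.51 | 41.5% | 63.2% | 70.8% | 8 | 29 |
| 0.8 | 0.40 | 0.36 | 41.5% | 81.5% | 85.6% | 4 | 44 |
| 0.9 | 0.20 | 0.19 | 41.5% | 98.5% | 98.9% | <1 | 57 |

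Losses are in percentage points against ANCOVA. Simulation of 60,000 trials per correlation agrees within 1 point.

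**Pairwise 95% CI half-width**, t(0.975) × √(2f/25) with t = 1.99, in SD units and before any multiplicity correction:

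- raw: 0.56 throughout
- change: 0.67, 0.56, 0.44, 0.36, 0.25
- ANCOVA: 0.54, 0.49, 0.40, 0.34, 0.25

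**The conditional reading.** Suppose ANCOVA is used only after a baseline test with p < 0.05. This trigger is an assumption, as the plan gives none. Under randomisation it fires in about 5% of trials, so the fallback test decides nearly every time. In the same simulation:

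- raw fallback: power 41–43% at every ρ; type I error 4.8, 4.6, 3.7, 3.2, 2.4%
- change-score fallback: power 31, 41, 64, 82, 99%; type I error 4.1, 4.6, 4.7, 4.8, 4.8%

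Nearly all of ANCOVA's gain over the fallback test is lost, and the type I error falls below 5% rather than rising above it.

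**The case against.** The strongest reply is that the plan may already do what is asked. The lines of section 8 follow a pattern of topic then method, so the ANCOVA line can fairly be read as covering swelling in every case. That reading is plausible, and under it swelling loses no precision. It is not certain, however, and it still leaves the covariate unnamed and the standing of the general test unsettled.

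A reader might infer that trismus has no baseline adjustment of any kind. The documents do not support that. The repeated-measures ANOVA line could cover trismus, and a group-by-time contrast with baseline as one of the times compares changes from baseline. What stands is narrower: no covariate adjustment is stated, the contrast is not named, and the Friedman alternative compares times within patients, not arms.

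A reader might also take the 29 to 57 point losses as the likely cost. They arise only if raw post-operative values are tested and the correlation is 0.7 or more. Facial distances measure swelling only in relation to the pre-op value, so a change-based test is the more natural unadjusted reading. The change-score loss is therefore the one to lead with.

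Finally, a reader might infer bias, or a choice of whichever p-value is smaller. Randomisation rules out the first for the unadjusted comparison, and nothing in the plan states the second.

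**Conclusion.** The concern holds as a gap in specification that should be fixed. The text does not settle whether ANCOVA is the between-arm analysis of swelling, and it states no covariate adjustment for trismus. Those findings rest on the wording alone.

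The size rests on assumptions that the documents cannot confirm: a 0.5 SD shift in one arm, equal SDs, and the correlation. If changes would otherwise be tested, the loss is at most about 14 points of power over the range examined, and 8 or fewer at correlations of 0.7 and above. It is larger at those correlations only if raw values are tested. If the line already means ANCOVA always, the precision loss is confined to trismus, and what remains for swelling is clarification. Confidence in the size is medium.

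**What to change.** Replace the ANCOVA line with:

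> Swelling and trismus at Day 2 and Day 7 are compared between arms by ANCOVA with the pre-op value of the same measure as covariate, in all cases, whether or not imbalance is observed. For swelling this is the primary between-arm analysis. Adjusted mean differences with 95% CI for H-PRF versus L-PRF and H-PRF versus control come from the same model, with Bonferroni adjustment.

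Bonferroni is already named in section 8 for the repeated-measures comparisons, and the two contrasts follow the primary objective in section 2. In addition:

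- State one swelling measure, used as both outcome and covariate.
- If residuals are clearly non-normal, report Quade's rank ANCOVA as a sensitivity analysis. Do not switch the primary test on a Shapiro-Wilk result.
- Keep the unadjusted ANOVA or Kruskal-Wallis result as supportive, and say whether it uses raw or change values.
- The missing-data line already reads "No missing data expected (all 75 randomized completed", so date the change and label it post hoc if outcome data had been seen.

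The sponsor must separately state which day carries the primary test; this wording does not settle that.

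The cost is one error degree of freedom (71 instead of 72), the SAP wording and a dated disclosure. Both baselines are already collected and ANCOVA is already in the plan, so no new data are needed.
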